## 2.0 Background

85% of stroke cases result in reductions in motor function, and this has a severe negative impact on daily living(1, 2). Motor rehabilitation training paradigms, such as task-specific training are common interventions to restore function in the affected limbs(3-7). Neuromodulation techniques such as transcranial magnetic stimulation (rTMS) are becoming a widely used tool to augment motor training. rTMS is most commonly used to modulate cortical excitability in the motor cortex of individuals receiving motor rehabilitation training (17, 18) and is also used to treat a variety of non-motor stroke symptoms such as depression(24). rTMS is a promising tool for neurorehabilitation, however its cortical effects are transient and behavioral benefits aren't seen for several weeks. There is a need for noninvasive

neuromodulatory techniques that can induce robust changes in cortical excitability to facilitate motor recovery after stroke and enhance and accelerate the neuroplastic changes induced by rTMS alone.

[name] (PI) and the team at the MUSC Brain Stimulation Lab have pioneered a noninvasive form of vagus nerve stimulation (VNS) known as transcutaneous auricular vagus nerve stimulation (taVNS). Our group demonstrated taVNS activates the afferent vagal system by using cardiac effects as a reliable biomarker to determine optimal stimulation parameters. Following the optimization of the parameter space, [name] conducted a novel concurrent taVNS/fMRI study exploring the direct brain effects of taVNS which revealed activation of the vagal afferent network induced by stimulation of the ABVN(25). This taVNS system can rapidly translate the promising basic animal studies revealing the neuroplasticity effects of paired-VNS, and a small open-label trial of paired taVNS is planned at MUSC later this year.

The research team is poised to develop a unique, novel, multimodal form of brain stimulation – combining both taVNS and TMS in a time dependent, synchronized manner. We plan to develop this taVNS/TMS system as Aim 1 of this proposal. Critical to understanding the facilitatory effects of pairing taVNS with TMS is the underlying principle of timing the paired stimulus which be better understood. Aim 2 explores the timing effects of paired taVNS/TMS in a classic MEP paradigm, which can help elucidate whether paring of stimulation is critical to the excitability changes. This proposal aims to create a concurrent taVNS/TMS system that can administer both paired- and unpaired- taVNS/TMS stimulation to the motor cortex and facilitate cortical excitability. We will subsequently use this system to investigate whether the timing of taVNS is critical to inducing motor cortex excitability.

#### **rTMS-induced increases in cortical excitability improve functional outcomes post-stroke**

Repetitive transcranial magnetic stimulation (rTMS) is a safe, noninvasive form of cortical brain stimulation that transiently induces neurophysiologic changes. When delivered at sub-threshold intensity to the motor cortex has been used to correct post-stroke interhemispheric-imbalance by either reducing excitability in the contralateral motor cortex or increasing excitability in the ipsilateral motor cortex. (17, 18).

Studies have demonstrated that single sessions of high frequency stimulation (20Hz) of the motor cortex elicits transient increases in MEP size. This modulation of cortical excitability makes rTMS an exciting tool for motor rehabilitation, as motor cortex excitability is involved in the learning of motor skills (26, 27). rTMS is a safe method of inducing motor cortex excitability and is in neurorehabilitation to either inhibit contralateral motor cortex or excite ipsilateral motor cortex in order to restore interhemispheric competition post-stroke.

#### **Transcutaneous Auricular Vagus Nerve Stimulation (taVNS) may facilitate neuroplasticity:**

Cervically implanted vagus nerve stimulation (cVNS) is an invasive form of neuromodulation which has been demonstrated to induce broad downstream neuroplastic cellular effects. These effects are driven by the locus coeruleus (LC) which serves as the main entry of the vagus nerve into the central nervous system. Lesions to LC inhibit this noradrenergic-driven neuroplasticity(28, 29). VNS is an influencer of neural plasticity when paired with specific behavior (30-33).

The auricular branch of the vagus nerve (ABVN) is the target of a novel form of noninvasive vagus nerve stimulation known as transcutaneous auricular vagus nerve stimulation (taVNS)(11)(14, 16, 29-34). [name] (PI) and the team at the MUSC Brain Stimulation Lab have pioneered several of the early studies demonstrating the biological effects of taVNS. As a cost-effective, noninvasive alternative to implantable cVNS we believe taVNS can mimic the effects of cVNS and be easily combined to enhance neuroplasticity.

#### **Pairing taVNS with TMS might synergistically increase the effects of TMS alone**

[figure not shown]
Rat models of VNS-paired therapy have demonstrated that timing is critical to the neuroplastic effects of VNS. Rehabilitation training without VNS takes a long time, and VNS alone fails to restore the behavior without the paired training. Delivering VNS immediately following training fails to enhance the training. Therefore, it is important to synchronize stimulation precisely with the paired training.

Aim 1 of this proposal establishes a computerized system that can synchronize two forms of neuromodulation – TMS and taVNS. Using this system, we will investigate whether the timing of taVNS impacts the cortical excitability effects of TMS alone.

### 3.0 Intervention to be studied

We will be using a combined taVNS/TMS system that will deliver taVNS with TMS training in a healthy population. The rational and overview is described below:

#### **Pairing taVNS with TMS**

Aim 1 of this study will establish a computerized system that facilitates the intricately timed paring of TMS and taVNS in healthy individuals. High frequency rTMS is a safe form of neuromodulation that is FDA-approved for depression and OCD. High-frequency TMS delivered to the motor cortex has been demonstrated to facilitate cortical plasticity.

taVNS is a safe form of cranial nerve stimulation that has been developed at MUSC by the PI of this project and is actively being used in several MUSC clinical trials exploring its use as a potential treatment for neuropsychiatric disorders. taVNS is also an enhancer of neuroplasticity.

This study will combine two safe, validated forms of neuromodulation delivered either concurrently (paired) or independently (unpaired).

#### **Motor-Evoked Potentials.**

**MEP Recordings.** EMG recordings using Ag/Ag Chloride electrodes will be placed on the subject's hand muscle in order to record motor excitability. The EMG recording electrodes will be connected to a standard CED (Cambridge Electronics Device) amplifier and pre-amplifier. Spike2 software will be used to analyze and record the MEPs. The level of stimulation required to produce a MEP of 1mV will be determined prior to collecting baseline MEPs. Baseline MEPs will be collected at the pre-determined stimulation output for 1mV. Another series of pulses will be analyzed in comparison with the first. If the average amplitude is within 25%, we will proceed with experiment. If not, another series of baseline pulses will be obtained repeating the above process, up to 4 times. If the baseline remains highly variable, the participant will be withdrawn. Following rTMS stimulation, the same pattern of single pulses will be recorded at 0, 10, 20, 30..

The key assumption that underlies the use of MEP measurements as a "read-out" of upstream processes influencing the motor system is that the amplitude of MEPs recorded (via EMG) from peripheral muscles is a product of top-down influences on M1 (such as attention/volitional control), combined with changes in excitatory/inhibitory pre-synaptic (inter)neuronal balance (i.e. due to rTMS at the stimulation site), and the post-synaptic excitability of corticospinal output projections (Bestmann and Krakauer, 2015). This method has been well-established as safe and reliable in the field of TMS research and in the brain stimulation laboratory.

[figure not shown]
**Neuronavigation.** Brainsight Neuronavigation equipment and software will be used (<https://www.rogue-research.com/tms/brainsight-tms/>) to help ensure that the stimulation site remains unchanged during and between recordings and thereby decrease MEP variability.

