## 1.0 Objectives / Specific Aims

The majority of patients suffering from stroke have functional motor impairments that negatively affect their mobility and daily life activities causing a low overall quality of life(1, 2). The most effective way to reduce these motor deficits is with task-specific rehabilitation training(3-7). Recent studies show that noninvasive brain stimulation can enhance task-specific training(8-10). Specifically, repetitive transcranial magnetic stimulation (rTMS) can noninvasively modulate the primary motor cortex(11-13). 1Hz rTMS has a cortically suppressive effect(14), whereas 10 and 20Hz stimulation paradigms induce cortical excitability(11, 12). Increases in excitability last between 10-60 minutes depending on the form of stimulation. These effects are likely long-term depression (LTD) and long-term potentiation (LTP) like neuroplasticity states, as pharmacological NMDA receptor blockade prevents these TMS-induced changes(15).

rTMS is emerging as a potential rehabilitation tool – when delivered to the motor cortex, rTMS can correct post-stroke interhemispheric-imbalance by either reducing excitability in the contralateral motor cortex with 1Hz rTMS(16) or increasing excitability in the ipsilateral motor cortex using 10 and 20Hz rTMS(17, 18). Findings from these studies suggest that rTMS may develop into a promising adjuvant to conventional motor rehabilitation, however a recent large-scale trial was negative however, showing that more work is needed to understand how best to use rTMS for stroke motor recovery.

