### Stimulation Parameters.

**rTMS:** 20 Hz rTMS will be delivered (using Magventure X100 system) to the motor hot spot of the left M1

region at 90% of rMT for 2.5 seconds ON and 10 seconds OFF. This will be repeated 40 times, for a total of 2,000 pulses of stimulation over 20-minutes. The stimulation target will be digitally marked using Brainsight neuronavigation for inter- and intra-session targeting validation.

**taVNS:** taVNS will be delivered (using a Digitimer constant current stimulation system) at the optimal stimulation parameters determined by our group (25Hz, 500us pulse width, 200% perceptual threshold) targeting the left anterior wall of the ear canal at a 50% duty cycle for 20 minutes.

**Paired taVNS/TMS:** We will synchronize taVNS with rTMS using MATLAB written software (Figure 2a). This software will deliver active/sham taVNS (25Hz, 500us PW, 200%PT) concurrently with active/sham 20Hz rTMS (2.5s ON, 10s OFF, 90% rMT) targeting the left M1 region (Figure 2b).

**Unpaired taVNS/TMS:** In this condition, active 20Hz rTMS (2.5s ON, 10s OFF, 90% rMT) will be delivered with active taVNS will be delivered in 2.5s trains during the rTMS using MATLAB written software. This software will deliver taVNS (25Hz, 500us PW, 200%PT) concurrently with 20Hz rTMS (2.5s ON, 10s OFF, 90% rMT) (Figure 2b).

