### Collected Measures :

#### MEPs using the Motor Cortex Excitability Recording Paradigm

Resting and active motor threshold will be found using PEST, and automated algorithm used to determine threshold. EMG recordings using Ag/AgCl electrodes will be placed on the subject's abductor pollicis brevis (APB) muscle in order to record motor evoked potentials (MEPs). The EMG recording electrodes will be connected to a standard Cambridge Electronics Device (CED) MEP system and MEPs will be recorded and analyzed with the associated Spike2 software. The level of stimulation required to produce a MEP of 1mV will be determined prior to collecting baseline MEPs. Up to 80 Baseline MEPs will be collected at the pre-determined stimulation output for 1mV. After the 20-minute randomized stimulation condition, up to 40 MEPs will be collected immediately after stimulation and at 10 minute intervals for 30 minutes.

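### The listed rTMS trains do not fill the stated 20 minutes, so time zero for the post-stimulation MEPs is open by 0 to about 12 minutes

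*Combined protocol and SAP*

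**What the plan says.** Section 10.0, Stimulation Parameters, describes 20 Hz rTMS over the left motor cortex, with its timing given as "region at 90% of rMT for 2.5 seconds ON and 10 seconds OFF", and continues: "This will be repeated 40 times, for a total of 2,000 pulses of stimulation over 20-minutes". In the same section the taVNS paragraph has taVNS "targeting the left anterior wall of the ear canal at a 50% duty cycle for 20 minutes". The paragraph on the paired condition has the software give taVNS, active or sham, together with the rTMS trains, active or sham.

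The Study Design paragraph of section 10.0 also gives each stimulation condition a length of 20 minutes.

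The post-stimulation MEPs are timed in four places:

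- Section 3.0, Motor-Evoked Potentials: "Following rTMS stimulation, the same pattern of single pulses will be recorded at 0, 10, 20, 30".
- Section 10.0, Collected Measures: "After the 20-minute randomized stimulation condition, up to 40 MEPs will be collected immediately after stimulation and at 10 minute intervals for 30 minutes".
- Section 4.0, Study Endpoints: ten-minute steps after stimulation, with details left to the study design section.
- Section 10.0, Study Design: directly after stimulation, then every ten minutes up to 30 minutes.

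On the persistence of the effect, section 1.0 says: "Increases in excitability last between 10-60 minutes depending on the form of stimulation".

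**The concern.** The spacing of the MEP blocks is consistent throughout. The event from which they are counted is not. One section starts the clock when rTMS ends, another when the 20-minute condition ends, and two say only that it follows stimulation. Every condition combines two modalities, active or sham, so the end of stimulation is a single event only if both stop together or one of them is named.

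This would be harmless if the stimulation timing were clear, but the rTMS paragraph contradicts itself on how long rTMS lasts. A team that programs the listed trains and also keeps a 20-minute condition could record the block labelled 0 minutes well after the last rTMS train.

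MEP amplitude is the only endpoint family, and its expected after-effect is short. If rTMS effects were read late and taVNS effects read at once, two comparisons would be affected: Aim 1's expectation that taVNS alone does less than rTMS alone, and Aim 2's comparison of the paired condition with taVNS alone.

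**Working it through.** **Inputs**, all from section 10.0, Stimulation Parameters: 20 Hz, 2.5 s ON, 10 s OFF, 40 trains, 2,000 pulses and 20 minutes for rTMS; 20 minutes at a 50% duty cycle for taVNS.

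**Step 1. Reproduce the pulse count.** Pulses = frequency × ON time × trains = 20 × 2.5 × 40 = 2,000. This agrees with the plan.

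**Step 2. Reproduce the duration.** Duration = trains × (ON + OFF) = 40 × 12.5 s = 500 s = 8 min 20 s. The plan says 20 minutes, so this does not reproduce. Two other readings do not help:

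- No OFF period after the last train: 40 × 2.5 + 39 × 10 = 490 s = 8 min 10 s.
- 10 s taken as the whole cycle: 40 × 10 = 400 s = 6 min 40 s.

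To show the size of the mismatch only, and not as a proposal: 40 trains in 20 minutes would need a cycle of 1,200 / 40 = 30 s, and a 12.5 s cycle kept up for 20 minutes would give 1,200 / 12.5 = 96 trains and 96 × 50 = 4,800 pulses. Train count, ON/OFF timing and duration cannot all be right.

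**Step 3. Carry this to the MEP clock.**

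| Reading | rTMS ends | Condition ends | Gap between the two anchors |
|---|---|---|---|
| rTMS lasts the stated 20 minutes | 20:00 | 20:00 | 0 |
| Trains as listed, whole condition ends with them | 8:20 | 8:20 | 0 |
| Trains as listed, condition goes on to 20 minutes | 8:20 | 20:00 | 1,200 − 500 = 700 s = 11 min 40 s |

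Counted from the last pulse instead of the last full cycle, the gap in the third row is 1,200 − 490 = 710 s = 11 min 50 s.

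**Step 4. What the third row would mean.** Counting from the end of the condition, the four blocks fall 11:40, 21:40, 31:40 and 41:40 after the last rTMS cycle. Counting from the end of rTMS, the first two blocks fall at 8:20 and 18:20 of the session, both before a 20-minute taVNS course would end.

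**Step 5. Does taVNS outlast rTMS?** The text points both ways. The taVNS paragraph gives 20 minutes at a 50% duty cycle. The paired paragraph ties taVNS to the rTMS trains, whose duty cycle is 2.5 / 12.5 = 20%. These are different patterns, and the text does not say which one governs the condition with sham rTMS and active taVNS.

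**Step 6. Can the bias be sized?** Not from the documents. As an illustration under assumed shapes, compare the mean effect at 0, 10, 20 and 30 minutes with the mean 11.67 minutes later. For an effect falling in a straight line to zero at 10, 30 or 60 minutes, the late mean is 0, 0.44 or 0.74 of the prompt one. For a flat effect that stops at 45 or 60 minutes, the ratio is 1. The answer runs from total loss to no loss according to the assumption, so no single figure is offered.

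**The case against.** The strongest reply is that there is only one clock. The rTMS paragraph itself says the pulses are spread over 20 minutes; on that statement the end of rTMS and the end of the condition coincide and the gap is zero. Nothing in the text says that rTMS stops early while the condition continues, or that there is a wait before the first MEPs. Every condition includes active or sham rTMS, so counting from the end of rTMS may be ordinary shorthand for the end of the session.

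Most of this stands. A reader might infer that sections 3.0 and 10.0 set two clocks that are 11 min 40 s apart. The documents do not show that: the gap needs the listed trains and a condition that runs on to 20 minutes, and it takes one side of a contradiction as fact.

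A reader might also infer an established bias between rTMS and taVNS. That is not shown either, because the paired paragraph has both modalities, active or sham, running together; on that reading they end together in every condition, including taVNS alone.

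Nor can a loss of power be derived. The documents give no decay shape, assign no after-effect duration to 20 Hz rTMS, and state no within-person correlation. A calculation that shrinks every contrast equally would also be at odds with a lag that differs between conditions.

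What the reply does not remove is the mismatch between 8 min 20 s and 20 minutes. Nor does correcting that arithmetic define time 0: if rTMS were stated as 8 min 20 s and taVNS left at 20 minutes, the two anchors would then truly differ.

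**Conclusion.** The concern holds as a contradiction in stimulation timing that leaves the endpoint's time zero undetermined. The listed trains take 8 min 20 s (8 min 10 s without the last OFF period) against a stated 20 minutes. The block labelled 0 minutes may therefore come at once or as much as about 11 min 40 s after the last rTMS train, depending on how the passages are reconciled. The arithmetic needs no assumption beyond the plan's own figures; that a lag would actually occur is conditional on the third reading in the table.

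If it did occur, it could understate rTMS effects relative to taVNS, because nearly 12 minutes is long on a scale of 10 to 60 minutes. The size of that effect is not computable from the documents. The plan's sample-size statement does not depend on this point. The figures to which sections 4.0 and 10.0 refer are not shown in the text available here, and they may make the intended timing clearer. The matter should be settled before data are collected, but it does not undermine the design.

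**What to change.** 1. Reconcile the train count, the ON/OFF timing and the 20-minute duration in section 10.0, Stimulation Parameters, with the 20-minute conditions in Study Design and Collected Measures. State how the general taVNS paragraph and the concurrent delivery in the paired paragraph fit together in each condition. Which schedule is intended is for the sponsor to say; none is proposed here.
2. Use one anchor in section 3.0 (Motor-Evoked Potentials), section 4.0, and section 10.0 (Study Design and Collected Measures): time 0 is the end of the last stimulation train, active or sham, of either modality, applied identically in all conditions, with MEP blocks starting 0, 10, 20 and 30 minutes later.
3. At every visit, log the clock time of the last rTMS train, the last taVNS train and the first pulse of each MEP block. A common anchor does not by itself rule out a lag for one modality; the logged times would show whether there is one and how large it is.

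The cost is protocol wording and a few timestamps per visit, with no added visits or participants.

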## 4.0 Study Endpoints

This figure describes the data collected and the endpoints that will be utilized. The endpoints revolve around motor physiology outcomes (Motor Evoked Potentials - MEPs) at baseline as well as at 10-minute increments post-stimulation

The MEP recordings will be used to track motor excitability outcomes.

More details about endpoints are described in the study design section.

## 5.0 Inclusion and Exclusion Criteria/ Study Population

**Inclusion Criteria:** Age 18-80, endorsing good health with no history of mental or physical illness or implanted metal in their body above the level of the neck.

**Exclusion Criteria:** Participants will be excluded for the following: no TMS-induced motor cortex excitability changes in response to 20Hz motor cortex rTMS, any recent psychiatric or physical illness; history of CNS disease, concussion, overnight hospitalization, or other neurologic sequelae, tumors, seizures, frequent or severe headaches; any psychotropic medication taken within 5 half-lives of procedure time; abuse or dependence of drugs (excluding nicotine and caffeine), currently taking medications that lower the seizure threshold; taking any of the stimulants, thyroid medication, or steroids; implanted devices/ferrous metal of any kind; history of seizure or seizure disorder; or inability to determine motor threshold, and TMS resting motor thresholds over 65% of total machine output assessed on experimental visit 1. Pregnant females and children under the age of 18 will be excluded for safety reasons. No vulnerable populations or special classes of subjects will be considered for participation.

## 6.0 Number of Subjects

**Total Planned Enrollment:** up to 40 healthy individuals

Healthy individuals of all ethnic and racial categories will be accepted into this study protocol. No preference will be given based on race, gender or ethnicity.

## 7.0 Setting

This study will be conducted at the MUSC Brain Stimulation Lab in the MUSC Institute of Psychiatry. The PI of this study has an office on the floor and is directly accessible to medical and professional staff for the safety of participants.

## 8.0 Recruitment Methods

Recruitment will be conducted using IRB-approved e-mail blasts (to students and staff), and word of mouth.

## 9.0 Consent Process

Written informed consent will be obtained from the participant by the PI or designated study team personnel. Consent process will occur at the MUSC Brain Stimulation Lab. Only individuals who pass an initial phone eligibility screening will be eligible to consent in person. This consent will happen on or before visit 1.

